## 8.4.5.2. Exposure During Breastfeeding

An EDB occurs if:

- A female participant is found to be breastfeeding while receiving or after discontinuing study intervention.
- A female nonparticipant is found to be breastfeeding while being exposed or having been exposed to study intervention (ie, environmental exposure). An example of environmental EDB is a female family member or healthcare provider who reports that she is breastfeeding after having been exposed to the study intervention by ingestion or skin contact.

The investigator must report EDB to Pfizer Safety within 24 hours of the investigator's awareness, irrespective of whether an SAE has occurred. The information must be reported using the CT SAE Report Form. When EDB occurs in the setting of environmental exposure, the exposure information does not pertain to the participant enrolled in the study, so the information is not recorded on a CRF. However, a copy of the completed report is maintained in the investigator site file.

An EDB report is not created when a Pfizer drug specifically approved for use in breastfeeding women (eg, vitamins) is administered in accordance with authorized use. However, if the infant experiences an SAE associated with such a drug, the SAE is reported together with the EDB.

# 8.4.5.3. Occupational Exposure

The investigator must report any instance of occupational exposure to Pfizer Safety within 24 hours of the investigator's awareness using the CT SAE Report Form regardless of whether there is an associated SAE. Since the information about the occupational exposure does not pertain to a participant enrolled in the study, the information is not recorded on a CRF; however, a copy of the completed report is maintained in the investigator site file.

# 8.4.6. Cardiovascular and Death Events

Not applicable.

# 8.4.7. Disease-Related Events and/or Disease-Related Outcomes Not Qualifying as AEs or SAEs

Not applicable.

#### 8.4.8. Adverse Events of Special Interest

Not applicable.

# 8.4.8.1. Lack of Efficacy

This section is not applicable because efficacy is not expected in the study population.

# 8.4.9. Medical Device Deficiencies

Not applicable.

# 8.4.10. Medication Errors

Medication errors may result from the administration or consumption of the study intervention by the wrong participant, or at the wrong time, or at the wrong dosage strength.

Medication errors are recorded and reported as follows:

Recorded on the Medication Error Page of the CRF	Recorded on the Adverse Event Page of the CRF	Reported on the CT SAE Report Form to Pfizer Safety Within 24 Hours of Awareness
All (regardless of whether associated with an AE)	Any AE or SAE associated with the medication error	Only if associated with an SAE

Medication errors include:

- Medication errors involving participant exposure to the study intervention;
- Potential medication errors or uses outside of what is foreseen in the protocol that do or do not involve the study participant.
- The administration of expired study intervention;
- The administration of an incorrect study intervention;
- The administration of an incorrect dosage;
- The administration of study intervention that has undergone temperature excursion from the specified storage range, unless it is determined by the sponsor that the study intervention under question is acceptable for use.

Whether or not the medication error is accompanied by an AE, as determined by the investigator, such medication errors occurring to a study participant are recorded on the medication error page of the CRF, which is a specific version of the AE page and, if applicable, any associated serious and nonserious AE(s) are recorded on the AE page of the CRF.

In the event of a medication dosing error, the sponsor should be notified within 24 hours.

Medication errors should be reported to Pfizer Safety within 24 hours on a CT SAE Report Form **only when associated with an SAE**.

## 8.5. Pharmacokinetics

Blood samples of approximately 4 mL, to provide approximately 1.5 mL of plasma, will be collected for measurement of plasma concentrations of etrasimod as specified in the SoA. Instructions for the collection and handling of biological samples will be provided in the laboratory manual or by the sponsor. The actual date and time (24-hour clock time) of each sample will be recorded.

The actual times may change, but the number of samples will remain the same. All efforts will be made to obtain the samples at the exact nominal time relative to dosing. Collection of samples up to and including 10 hours after dose administration that are obtained within 10% of the nominal time relative to dosing (eg, within 6 minutes of a 60-minute sample) will not be captured as a protocol deviation, as long as the exact time of the collection is noted on the source document and the CRF. Collection of samples more than 10 hours after dose administration that are obtained  $\leq 1$  hour away from the nominal time relative to dosing will not be captured as a protocol deviation, as long as the exact time of the collection is noted on the source document and the CRF. This protocol deviation window does not apply to samples to be collected more than 10 hours after dose administration at outpatient/follow-up visits with visit windows.

Samples will be used to evaluate the PK of etrasimod. Samples collected for analyses of etrasimod plasma concentration may also be used to evaluate safety or efficacy aspects related to concerns arising during or after the study, for protein binding, metabolite identification and/or evaluation of the bioanalytical method, or for other internal exploratory purposes. The exploratory results may not be reported in the CSR.

Genetic analyses will not be performed on these PK samples.

Samples collected for measurement of plasma concentrations of etrasimod will be analyzed using a validated analytical method in compliance with applicable SOPs.

The PK samples must be processed and shipped as indicated in the instructions provided to the investigator site to maintain sample integrity. Any deviations from the PK sample handling procedure (eg, sample collection and processing steps, interim storage or shipping conditions), including any actions taken, must be documented and reported to the sponsor. On a case-by-case basis, the sponsor may make a determination as to whether sample integrity has been compromised.

Any changes in the timing or addition of time points for any planned study assessments must be documented and approved by the relevant study team member and then archived in the sponsor and site study files, but will not constitute a protocol deviation. The IRB/EC will be informed of any safety issues that require alteration of the safety monitoring scheme or amendment of the ICD.

Additional blood samples of approximately 0.5 mL using a micro sampling device (Tasso) will be collected, to provide approximately 0.25 mL serum into appropriately labeled tubes for measurement of etrasimod at selected timepoints as specified in the SoA.

The "Tasso device" is an integrated capillary blood collection device. This part of the study is designed to validate etrasimod PK concentrations in capillary blood collected using the Tasso device against PK samples collected from traditional venous blood samples. Findings from the validation may enable patient-centric blood sampling using this innovative device in future etrasimod pediatric clinical studies.

Blood samples from capillary blood vessels, collected using the Tasso device, should be timed as close as possible to the collection of etrasimod blood samples. The Tasso device should be attached to the upper arm. Details for collection and handling of the samples will be provided in the laboratory manual.

The blood samples collected using Tasso device will be used for internal exploratory purposes for comparing the etrasimod concentrations between venous and capillary blood.

The results from this comparison will be documented in a separate internal bioanalytical report and will not be included in the CSR.

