	dosing without major clinically relevant cardiac safety events.	
Reproductive and developmental toxicity.	The effects of etrasimod on human fertility and embryonic development are unknown.	WOCBP who are pregnant, lactating, or breastfeeding will be excluded from this study.
	Nonclinical reproductive and developmental toxicity studies of etrasimod combined with data and knowledge on the role of S1P 1 in vascular embryogenesis demonstrate embryo fetal toxicity of etrasimod if used during pregnancy. Etrasimod is potentially teratogenic in humans with a low genotoxic potential. There is no margin of safety for these findings compared to therapeutic exposure range. Etrasimod should not be given to women who are pregnant, lactating or breastfeeding	

WOCBP will be eligible only if she and her partner(s) agree(s) with the contraceptive method as described in Section 10.4.4 throughout the study period and for at least 28 days after the last dose of etrasimod.

Males with female partners of childbearing potential must agree to use contraception throughout the study period and for at least 28 days after the last 28 days after the last dose of etrasimod.

	Study Procedures Blood Collection for PK	
Extravasation, bruising, local discomfort	Collection of 14 PK plasma samples per period per sequence	Use of highly qualified nurses, with venipuncture experience.
	Collection of 8 PK micro samples collected for Treatment A.	Use of alternating arms for adjacent time points can provide more resting and healing time for each arm between samplings.

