# **3. OBJECTIVES AND ENDPOINTS**

Objectives	Endpoints
Primary:	Primary:

 
To estimate the rBA of etrasimod 2 mg mini tablets mixed with water compared to etrasimod 2 mg clinical IR tablets under fasted conditions
 
To estimate the rBA of the etrasimod 2 mg mini tablets mixed with applesauce compared to the etrasimod 2 mg clinical IR tablets under fasted conditions
 
To estimate the rBA of the etrasimod 2 mg mini tablets mixed with chocolate pudding compared to the etrasimod 2 mg clinical IR tablets under fasted conditions
 
To estimate the rBA of the etrasimod 2 mg mini tablets mixed with chocolate pudding compared to the etrasimod 2 mg clinical IR tablets under fasted conditions
 
To estimate the rBA of the etrasimod 2 mg mini tablets mixed with yogurt compared to the etrasimod 2 mg clinical IR tablets under fasted conditions
 
	• Plasma AUC last , AUC inf and C max of etrasimod
Secondary:	Secondary:
• To evaluate the safety and tolerability of etrasimod in healthy participants	• Assessment of first dose HR reduction, TEAEs, clinical laboratory abnormalities, vital signs, PEs, and 12-lead ECGs
• To assess the palatability of etrasimod mini tablets mixed with water/applesauce/chocolate pudding/yogurt	• Assessment of palatability via questionnaire: mouth feel, bitterness, tongue/mouth burns, throat burn, and overall liking
Tertiary/Exploratory:	Tertiary/Exploratory:
• To characterize the PK parameters of etrasimod 2 mg mini tablets mixed with water or soft foods (applesauce, chocolate pudding, or yogurt) compared to etrasimod 2 mg clinical IR tablet	
 
Plasma etrasimod: t1/2, CL/F, Vz/F and Tmax of etrasimod
 

• To validate the PK measurement of etrasimod in capillary blood sample collected using micro sampling device against the PK measurement of etrasimod in venous blood samples.	• Plasma concentration of etrasimod obtained via micro sampling compared to venous sampling

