# 9.3.5. Micro Sampling and Venous Sampling

Etrasimod concentration at sampling time points,  $C_{max}$  and  $AUC_{0-24}$  from paired samples obtained via micro sampling and venous sampling will be compared. Individual participant

differences and % differences of concentrations by PK sampling time,  $C_{max}$  and  $AUC_{0-24}$  will be listed and summarized descriptively.

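### The micro sample is specified as serum, but its venous comparator and the named endpoint are plasma, so sampling site and matrix are aliased in every pair

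*Protocol*

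**What the plan says.** Protocol Section 8.5 describes two kinds of pharmacokinetic sample. The venous sample is plasma: "Blood samples of approximately 4 mL, to provide approximately 1.5 mL of plasma, will be collected for measurement of plasma concentrations of etrasimod". The Tasso capillary sample, about 0.5 mL of blood, is drawn "to provide approximately 0.25 mL serum into appropriately labeled tubes".

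The exploratory endpoint in protocol Section 3, repeated in SAP Section 2.2, is "Plasma concentration of etrasimod obtained via micro sampling compared to venous sampling". Section 8.5 describes this part of the study as "designed to validate etrasimod PK concentrations in capillary blood collected using the Tasso device against PK samples collected from traditional venous blood samples".

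On the assay, Section 8.5 says "Samples collected for measurement of plasma concentrations of etrasimod will be analyzed using a validated analytical method"; it names no method for the micro samples. For the analysis, protocol Section 9.3.5 and SAP Section 6.3.2 say that concentrations, Cmax and AUC0-24 "from paired samples obtained via micro sampling and venous sampling will be compared". Differences and percentage differences are listed and summarized descriptively. Neither section mentions a conversion between serum and plasma.

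**The concern.** The comparison is meant to show whether capillary sampling can stand in for venous sampling. Protocol Section 4.2.3 ties it to a future pediatric study in children as young as 2 years. If the capillary sample is serum and the venous sample plasma, two things change at once within each pair. A difference might come from the matrix rather than the sampling site. Agreement might come from two effects that cancel. The endpoint named in both documents, a plasma concentration from the micro sample, would also not have been measured. The sponsor could then carry a wrong explanation of the result into the pediatric program.

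**Working it through.** **Matrix by place in the documents**

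| Place | Capillary (Tasso) | Venous |
|---|---|---|
| Protocol 8.5 | serum, about 0.25 mL | plasma, about 1.5 mL |
| Protocol 3, exploratory endpoint | plasma | not named separately |
| SAP 2.2, exploratory endpoint | plasma | not named separately |
| Protocol 9.3.5 and SAP 6.3.2 | no matrix named, no conversion | no matrix named, no conversion |

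The only other research serum sample is the Prep B2 tube (protocol Section 8.7.1). It is drawn on Period 1 Day 1 only, for safety biomarkers. No venous serum is planned for an etrasimod assay, and no capillary plasma.

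**Number of pairs affected.** Protocol Section 2.3.1 gives the count per participant: "Collection of 8 PK micro samples collected for Treatment A". The Schedule of Activities lists predose and 1, 2, 4, 6, 8, 12 and 24 hours, so 1 predose and 7 postdose times. Section 4.1 gives 16 enrolled and 12 evaluable.

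- 16 enrolled: 16 × 8 = 128 pairs, of which 16 × 7 = 112 are postdose.
- 12 evaluable: 12 × 8 = 96 pairs, of which 12 × 7 = 84 are postdose.

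Predose pairs carry little information. Participants in Sequence 1 receive Treatment A first and have no drug on board. For the others, 9 days at a half-life of about 30 hours is 216/30 = 7.2 half-lives, and 2^(−7.2) is about 0.7% remaining from a preceding dose.

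**Identifiability.** Let c be the true capillary/venous ratio in a common matrix and m the serum/plasma ratio. Each pair estimates only the product:

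observed ratio = c × m

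Coded as intercept, site and matrix, every capillary row is (1, 1, 1) and every venous row is (1, 0, 0). The design has rank 2 for 3 parameters, however many pairs are collected. With one matrix for both samples, site is identifiable (rank 2 of 2). With an added venous serum sample at the paired times, site and matrix are both identifiable (rank 3 of 3).

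**What aliasing could do.** The documents give no value for m. The range 0.90 to 1.10 below is an assumption, for illustration only. Entries are 100 × (c × m − 1).

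| m (assumed) | c = 0.90 | c = 1.00 | c = 1.10 |
|---|---|---|---|
| 0.90 | −19.0% | −10.0% | −1.0% |
| 0.95 | −14.5% | −5.0% | +4.5% |
| 1.00 | −10.0% | 0.0% | +10.0% |
| 1.05 | −5.5% | +5.0% | +15.5% |
| 1.10 | −1.0% | +10.0% | +21.0% |

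The c = 1.00 column shows a pure matrix effect that would look like a device effect. The corner entries of −1.0% show near-agreement produced by two opposing 10% effects. If m = 1.00, there is no distortion.

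**The case against.** The strongest reply is that serum is a one-word slip for plasma. Both endpoint tables say plasma, and Section 8.5 itself speaks loosely of venous and capillary blood. It also leaves collection and handling details to the laboratory manual, which is not among the documents. If the manual specifies a plasma tube, there is no confounding and only a text error remains. This stands as a possibility. It does not remove the need to reconcile the text, because the serum wording has its own yield volume and a site or laboratory could reasonably follow it.

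A second reply is that the aim can be read as a method comparison: does the Tasso result agree with the conventional venous result? If the pediatric study used the same Tasso serum procedure, total disagreement would be the quantity of interest and its cause secondary. This also stands. A reader might infer from the aliasing that the objective cannot be answered at all. The documents do not support that, because total agreement can be estimated. What is lost is attribution to the sampling site, and the endpoint as named.

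Third, the protocol's silence on a serum assay or a serum-plasma bridge does not show that none exists. The micro-sampling work is to be reported in a separate bioanalytical report. The absence of a stated serum method is therefore a reason to clarify, not evidence of an unvalidated assay.

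Finally, the objective is exploratory, the analysis is descriptive, and the results stay out of the clinical study report. That limits the weight of the point but does not resolve the contradiction.

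**Conclusion.** The point holds as an inconsistency with a real consequence if Section 8.5 is followed literally. The plasma endpoint would not be collected, and site would be fully aliased with matrix in all 128 planned pairs (112 postdose; 96 and 84 with 12 evaluable participants). Only the combined difference between Tasso serum and venous plasma would be estimable.

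The conclusion assumes that serum means serum and that the laboratory manual does not override it. A reader might infer a device bias of 5% or 10%. The documents support no such figure: they give no serum/plasma ratio, and the bias may be nil. Nor is the relative bioavailability result in doubt, since the primary analysis uses venous plasma throughout.

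**What to change.** Change serum to plasma in protocol Section 8.5, and have the laboratory manual specify a Tasso plasma tube with the same anticoagulant as the venous pharmacokinetic sample. Sections 3 and 8.5 of the protocol and Section 2.2 of the SAP would then name one matrix. The cost is one word in the protocol and a tube type in the manual, with no added visits or blood.

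If serum is truly intended, reword the endpoint in protocol Section 3 and SAP Section 2.2 as capillary serum versus venous plasma, state the method used for serum, and limit the conclusion to total method agreement. This costs text only, but it gives up attribution to the sampling site.

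Do not replace the venous plasma sample with serum. Venous plasma under Treatment A is the reference for the primary analysis, so the replacement would damage that analysis, and keeping both would mean additional venous blood.

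Make the correction before the Treatment A samples are collected.

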# 8.6. Genetics

# 8.6.1. Specified Genetics

Specified genetic analyses are not evaluated in this study.

# 8.6.2. Retained Research Samples for Genetics

Retained Research Samples for Genetics are not collected in this study.

# 8.7. Biomarkers

# 8.7.1. Safety Biomarker Sample

A 10-mL blood sample (Prep B2) for serum will be collected as indicated in the SoA for safety biomarker work by the Innovative Medicines Initiative (IMI) Consortium. Biomarker data may be generated to increase understanding of safety events associated with study interventions.

# 8.8. Immunogenicity Assessments

Immunogenicity assessments are not included in this study.

# 8.9. Health Economics

Health economics/medical resource utilization and health economics parameters are not evaluated in this study.

#### 8.10. Palatability Assessments

Palatability assessment of the etrasimod mini tablets will be conducted in every period for Treatments B, C, D, E with the aid of a questionnaire (Appendix 9). The palatability assessment questionnaire will be administered to participants by trained staff using a colored copy of the questionnaire. After study intervention administration, participants will be asked to rate the mouth feel, bitterness, tongue/mouth burn, throat burn, and overall liking. The participants will rate the above within 1 minute (immediately) after dosing, before drinking water that is given as part of dosing, and at 5 minutes, 10 minutes, 20 minutes after dosing is fully completed.

See Appendix 9 for the details about the palatability assessment questionnaire.

# 9. STATISTICAL CONSIDERATIONS

Detailed methodology for summary and statistical analyses of the data collected in this study is outlined here and further detailed in the SAP, which will be maintained by the sponsor. The SAP may modify what is outlined in the protocol where appropriate; however, any major modifications of the primary endpoint definitions or their analyses will also be reflected in a protocol amendment.

### 9.1. Statistical Hypotheses

No statistical hypothesis will be tested in this study.

#### 9.2. Analysis Sets

For purposes of analysis, the following analysis sets are defined:

Participant Analysis Set	Description
Safety Analysis Set	All participants who take at least 1 dose of study intervention. Participants will be analyzed according to the product they actually received.
PK Concentration Set	All participants who take at least 1 dose of study intervention and in whom at least 1 concentration value is reported.
PK Parameter Set	All participants who take at least 1 dose of study intervention and in whom at least 1 of the PK parameters of interest are reported.

# 9.3. Statistical Analyses

The SAP will be developed and finalized before database lock and will describe the participant populations to be included in the analyses, and procedures for accounting for missing, unused, and spurious data. This section is a summary of the planned statistical analyses of the primary and secondary endpoints.

## 9.3.1. Efficacy Analyses

An efficacy analysis is not applicable to this study.

## 9.3.2. Safety Analyses

All safety analyses will be performed on the safety population.

AEs, ECGs, BP, pulse rate, and safety laboratory data will be reviewed and summarized on an ongoing basis during the study to evaluate the safety of participants. Any clinical laboratory, ECG, BP, and pulse rate abnormalities of potential clinical concern will be described. Safety data will be presented in tabular and/or graphical format and summarized descriptively, where appropriate.

Medical history and physical examination information, as applicable, collected during the course of the study, will be considered source data and will not be required to be reported, unless otherwise noted. However, any untoward findings identified on physical and/or neurological examinations conducted during the active collection period will be captured as AEs, if those findings meet the definition of an AE (Appendix 3). Data collected at screening that are used for inclusion/exclusion criteria, such as laboratory data, ECGs, and vital signs, will be considered source data, and will not be required to be reported, unless otherwise noted. Demographic data collected at screening will be reported.

